[figure not shown]

Efficacy of Intercostal CryoAnalgesia in Patients Undergoing Robot Assisted Anatomic Lung Resection

PROTOCOL SUMMARY

Synopsis

Title:	Efficacy of Intercostal CryoAnalgesia in Patients Undergoing Robot Assisted Anatomic Lung Resection
Short Title:	CryoNB in Robotic Lung Resection
Study Design:	Prospective randomized study
Study Objectives:	
The objectives are to determine if the addition of Cryo Nerve Block at the time of robot assisted thoracoscopic lung resection surgery will:
 
 Allow for improved postoperative analgesia as measured using Visual Analogue Scale (VAS) pain scores Allow for decreased post-operative pain medication (opioid) use Allow for accelerated recovery as measured by patient reported M.D. Anderson Symptom Inventory (MDASI) Questionnaire Increases the risk for development of neurogenic pain as measured by the Leeds Assessment of Neuropathic Symptoms and Signs (LANSS) pain scale
Number of Subjects:	40 (20 in each group)
Sites:	Single site – Froedtert Hospital/Medical College of Wisconsin Single surgeon – [name]
Study Population:	Patients undergoing robot assisted thoracoscopic anatomic lung resection (pneumonectomy, bilobectomy, lobectomy or segmentectomy)
Inclusion Criteria:	
 Age 18 - 85 years male or female Acceptable surgical candidate Willing and able to return for scheduled follow-up visits
Exclusion Criteria:	
 Patients undergoing or requiring conversion to thoracotomy Patients with chronic pain syndromes requiring treatment within the last year Patients with a history of illicit drug use Patients with a history of heavy alcohol use in the last five years as determined by the principal investigator Patients currently using opioids
Participant Duration:	Six months
Study Endpoints:	
Primary endpoints
 
 Visual Analogue Scale (VAS) Pain score on post-operative days 1-14, Day 30, Day 60, Day 90, Day 120, Day 150, Day 180 (or until a score of 0). Pain medication use daily for 21 days post-operatively 
Secondary endpoints
 
 M.D. Anderson Symptom Inventory Questionnaire on post-operative Day 1, Day 7, Day 14, Day 21, Day 30, Day 35, and Day 42 Leeds Assessment of Neuropathic Symptoms and Signs (LANSS) score at Post-Operative Day 30, Day 90, and Day 180

Schema

HYPOTHESIS

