The addition of Cryo Nerve Block to a standard postoperative pain regimen will improve analgesia and facilitate recovery following robot assisted thoracoscopic anatomic lung resection

SPECIFIC AIMS

This study will determine if the addition of Cryo Nerve Block during robot assisted thoracoscopic anatomic lung resection surgery will:

PRIMARY ENDPOINTS:

- Allow for improved postoperative analgesia as measured using Visual Analogue Scale (VAS) pain scores
- Allow for decreased post-operative pain medication (opioid) usage

SECONDARY ENDPOINTS:

- Allow for accelerated recovery as measured by patient reported M.D. Anderson Symptom Inventory (MDASI) Questionnaire
- Increases the risk for development of neurogenic pain as measured by the Leeds Assessment of Neuropathic Symptoms and Signs (LANSS) pain scale

RATIONALE FOR THE PROJECT

Thoracic surgical procedures are consistently reported to be among the most painful surgical incisions currently used.¹ Trauma to the skin, muscle, intercostal nerves, bones and pleura all contribute and lead to activation of various pain pathways including somatic, visceral, neurogenic and phrenic.¹ In the short term, this pain leads to ineffective cough and pulmonary hygiene resulting in respiratory complications and prolonged hospital stays while in the longer term it leads to prolonged recovery, delayed return to work and in some instances, chronic post thoracotomy pain syndromes.² Minimally invasive approaches such as standard thoracoscopy or robotic assisted thoracoscopy have certainly decreased some of this trauma as evidenced by decreased length of stays and decreased complication rates however even with these minimally invasive techniques, recovery to 80% of baseline is 25 days³ and 9.4% of patients are still using narcotics after 90-180 days.⁴

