Several options are available in the management of pain following thoracic surgery with a multimodal pain medicine approach being most common. Opioids, unfortunately, are a relatively large part of this approach and are often relied upon despite their relatively unfavorable adverse event profile and risk for addiction. Many of the other pain adjuncts often used with thoracotomies such as epidural catheters or intraoperatively placed pain catheters are not really reasonable when using minimally invasive approaches as the hospital length of stay is 1-2 days. Intercostal cryoanalgesia has been shown to be a safe and effective strategy for post-operative pain management in patients undergoing thoracotomy.^{5,6} Recent studies have demonstrated the beneficial effect of cryoanalgesia for post-thoracotomy pain in reduction of opioid requirement, reduction in post-operative pain scores, and superior pulmonary function (higher FEV1 and FVC values)⁵ and that it can produce temporary neurolysis for up to two months without long-term histological nerve damage.⁶ To date it has not been studied when using minimally invasive techniques whether it be standard thoracoscopy or robotic assisted thoracoscopy but it would stand to reason that it would be equally or maybe more effective in this patient population and truly maximize the benefits of a minimally invasive approach .

We therefore propose to assess whether intra-operative intercostal cryoanalgesia using the cryoICE® probe provides superior post-operative analgesia as compared to our current standard pain management strategy in patients undergoing robotic assisted thoracoscopic anatomic lung resection and allows for decreased opioid use and more rapid recovery.

PROJECT DESIGN AND PROTOCOL

DESIGN

This is a single center, single surgeon, prospective, randomized trial examining the addition of Cryo Nerve Block during robot assisted thoracoscopic anatomic lung resection surgery

SUBJECTS IN THE STUDY

40 total subjects will be enrolled in the study – 20 in each group

Inclusion Criteria

- Patients undergoing robot assisted thoracoscopic anatomic lung resection surgery
- Male or female age 18 or older
- Acceptable surgical candidate
- Willing and able to return for scheduled follow-up visits

Exclusion Criteria

- Patients undergoing or requiring conversion to thoracotomy
- Patients with chronic pain syndromes requiring treatment in the last year
- Patients with a history of illicit drug use

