Risks inherent to this study are those associated with the operative procedure of robot assisted thoracoscopic lung resection surgery. To date there have been no reports of acute adverse events with cryo nerve block.

DATA COLLECTED

As shown in the schema, the following data will be collected

Preoperatively – within 30 days of surgery

- Characteristics (Age, gender, race, marital status, ECOG function, height, weight, BMI, tobacco use, major comorbidities)
- Baseline VAS Score
- Baseline MDASI
- Baseline LANSS

Intraoperatively – at time of surgery

- Procedure
- Procedure duration
- Port placement
- Intraoperative complications
- Estimated blood loss (EBL)

Postoperatively – at designated time points

- Length of stay
- Chest tube duration
- Complications
- VAS pain scores daily on post-operative Days 1-14, Day 30, Day 60, Day 90, Day 120, Day 150, Day 180 (or until score of 0).
- Pain med usage daily for post-operative Days 1-21
- MDASI questionnaire on post-operative Day 1, Day 7, Day 14, Day 21, Day 30, Day 35, and Day 42
- LANSS score at Day 30, Day 90 and Day 180

A time frame of data collection points is shown below and the VAS scale, MDASI Questionnaire, and LANSS pain scale are included in the appendix.

Day	Characteristics	VAS	MDASI	LANSS	Pain meds
Baseline	X	X	X	X	X
0					
1		X	X		X
2		X			X
3		X			X
4		X			X

5		X			X
6		X			X
7		X	X		X
8		X			X
9		X			X
10		X			X
11		X			X
12		X			X
13		X			X
14		X	X		X
15					X
16					X
17					X
18					X
19					X
20					X
21			X		X
22					X
30 (+/- 2 days)		X	X	X	
35 (+/- 2 days)			X		
42 (+/- 2 days)			X		
60 (+/- 5 days)		X			
90 (+/- 5 days)		X		X	
120 (+/- 5 days)		X			
150 (+/- 5 days)		X			
180 (+/- 5 days)		X		X	

REFERENCES

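### VAS, a primary endpoint, stops at a score of 0, with no start day or confirmation rule; if cryo works and then wears off, late pain intensity goes unrecorded more often in the cryo arm

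*Protocol*

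**What the plan says.** VAS is listed as a primary endpoint in the Protocol's Synopsis and Specific Aims. Two places set its collection days, and both allow an early end. The Synopsis (Study Endpoints) has "Day 120, Day 150, Day 180 (or until a score of 0"), and the postoperative list under Data Collected has "Day 60, Day 90, Day 120, Day 150, Day 180 (or until score of 0"). Neither gives a start day for the rule, a confirmation requirement or a restart condition.

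The schedule table under Data Collected, introduced by "A time frame of data collection points is shown below", marks VAS on every one of these days through Day 180 with no stopping note.

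The other patient-reported measures have no such clause but do not cover the same ground:

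- Pain medication, the other primary endpoint: "Pain med usage daily for post-operative Days 1-21" (the table adds Day 22).
- MDASI, whose first item rates worst pain from 0 to 10 (Appendix III): last collected on Day 42.
- LANSS: "LANSS score at Day 30, Day 90 and Day 180". The form in Appendix IV scores neuropathic features and has no intensity rating.

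The Hypothesis is that cryo "will improve analgesia and facilitate recovery following robot assisted thoracoscopic anatomic lung resection". The Rationale says of cryoanalgesia that "it can produce temporary neurolysis for up to two months".

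**The concern.** The rule makes collection of a primary endpoint depend on that endpoint's own earlier values, and the trial's hypothesis is that those values differ by arm. If cryo lowers early pain, cryo patients reach 0 sooner and leave VAS while the block is active. If the effect then fades within the two months the Rationale mentions, any pain that returns falls where those patients are no longer asked. After Day 42, VAS is the only record of pain intensity.

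Five VAS visits (Days 60, 90, 120, 150 and 180) exist to describe this period. The Rationale also motivates the trial partly by late outcomes, noting that "9.4% of patients are still using narcotics after 90-180 days".

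An analysis plan can choose how to treat missing scores, but it cannot recover scores that staff were told not to collect. Separately, the rule can be applied in several ways, so the primary data could depend on how site staff read it.

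**Working it through.** The Protocol states no figure on this point, so there is nothing to reproduce. The check has two parts, both on assumed inputs.

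**1. How far the undefined start day matters**

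Let p be the chance of a 0 at one occasion and k the number of occasions before Day 60 at which a 0 counts. Treating occasions as independent, P(stopped before Day 60) = 1 - (1 - p)^k. If every day counts, k = 14 + 1 = 15 (Days 1-14 and Day 30). If only Day 30 counts, k = 1. The Protocol gives no p, so the values below are assumed.

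| p, control v cryo | k = 15: stopped | k = 15: left of 20 | k = 1: stopped |
|---|---|---|---|
| 0.02 v 0.05 | 26% v 54% | 14.8 v 9.3 | 2% v 5% |
| 0.05 v 0.10 | 54% v 79% | 9.3 v 4.1 | 5% v 10% |
| 0.10 v 0.20 | 79% v 96% | 4.1 v 0.7 | 10% v 20% |

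For example, 1 - 0.95^15 = 0.537 and 1 - 0.90^15 = 0.794. At p = 0.05 the start day alone moves control-arm stopping from 5% to 54%. Scores within a patient are correlated, so the k = 15 figures overstate stopping. They show direction and sensitivity only.

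**2. Bias at Day 90, with correlated scores**

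Simulation of 60,000 patients per arm on the 14 + 6 = 20 postoperative VAS days. All inputs are assumed:

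- Integer scores from 0 to 10.
- Control mean 4.5 on Day 1 and 1.0 on Day 180, falling linearly in log(day), linearly in day, or exponentially with half-life 7, 14 or 30 days.
- Cryo lower by 0.5, 1.0 or 1.5 points through Day 30, by a third of that at Day 60, and equal from Day 90.
- Between-patient SD 1, 1.5 or 2; day-to-day SD 1.

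This gives 5 x 3 x 3 = 45 combinations, with a true Day 90 difference of zero. Let Y be the Day 90 score and O = 1 if VAS is still being collected. Within an arm the full-data mean is E[Y]. Carrying zeros forward gives E[Y x O], an error of -E[Y x (1 - O)]. Observed-only gives E[Y | O = 1]. The likelihood-type estimate uses sequential regression within arm.

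Ranges over the 45 combinations (bias is cryo minus control, so negative favours cryo):

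| Rule | Still measured at Day 90, of 20 (cryo; control) | Zeros carried forward | Observed-only | Likelihood-type |
|---|---|---|---|---|
| One 0, from Day 1 | 2-18; 9-19 | -0.7 to -0.05 | +0.07 to +0.8 | -0.03 to +0.09 |
| One 0, from Day 30 | 4-19; 10-19 | -0.4 to -0.02 | +0.03 to +0.6 | -0.01 to +0.2 |
| Two 0s in a row, from Day 1 | not tabulated | -0.4 to -0.01 | +0.02 to +0.7 | not run |
| Two 0s in a row, from Day 30 | not tabulated | -0.2 to 0 | +0.01 to +0.4 | not run |

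With one 0 counting, control always keeps more patients: by about 1-8 of 20 from Day 1, and 0.3-6 from Day 30. With one 0 from Day 1, Day 90 scores above 0 that go unrecorded number about 1.5-11 per 20 in cryo and 0.7-5.5 per 20 in control.

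**Other effect patterns.** With no cryo effect, every estimate is within 0.02 of the full data. With a persistent effect (0.5 or 1.5 points, one-0 rule, true Day 90 difference -0.3 to -1.4), zeros carried forward is off by -0.18 to +0.16 and the likelihood-type estimate overstates the benefit by 0 to 0.5.

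**The case against.** The strongest reply is that stopping after a recorded 0 depends only on observed VAS. The scores are then missing at random by design, and a likelihood-based model chosen in the SAP should handle them. Its bias under wear-off is indeed small in the table above. This stands in part. But under a one-0 rule nobody is observed after a 0, so the model extrapolates from patients still in pain, and the collected VAS data cannot test that. Under a persistent effect the same approach overstates benefit by up to 0.5 points.

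The size may also be modest. The stopping clause follows Day 180, so a reading confined to the late visits is natural. With the rule from Day 30, the median zeros-carried-forward bias is about -0.14 points and is under 0.2 in 71% of combinations, against a full-data standard error of about 0.48 at 20 per arm. That is fair. It also shows that the answer depends on a reading the text leaves open.

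Other points carry some weight:

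- No passage says pain rises when neurolysis ends, and two months is an upper limit. The wear-off bias is conditional on that assumption.
- A table of marks may show only the maximum schedule, so text and table need reconciling but do not strictly conflict.
- The 9.4% figure is narcotic use, not pain intensity, and supports the importance of late VAS only indirectly.
- The schema figure is missing from the copy reviewed and might state a start day. That would settle one ambiguity and leave the clause in place.
- Stopping at 0 may be a deliberate way to spare pain-free patients. Clarifying the rule would remove the ambiguity but leave part of the unequal loss, as the two-0 rows show.

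**Conclusion.** The concern holds and should be fixed. The ambiguity is certain whatever cryo does: the text gives no start day, confirmation or restart rule for ending a primary endpoint. The unequal loss is conditional on cryo producing more early zeros, and the wear-off bias also requires the effect to fade. Under those conditions with a one-0 rule, the two simple analyses err in opposite directions in all 45 combinations: carrying zeros forward favours cryo and observed-only favours control. Their size runs from negligible to about 0.7-0.8 points on the 0-10 scale. These magnitudes rest entirely on assumed means, SDs and effects, so confidence is high in the wording gap and the direction, and low in any single number. LANSS would still capture neuropathic features on Days 90 and 180. What is lost is pain intensity after Day 42.

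**What to change.** Delete the parenthetical stopping clause after Day 180 in both places: the Synopsis (Study Endpoints) and the postoperative list under Data Collected. Add one sentence under the schedule table: VAS is collected on every marked day through Day 180, whatever the earlier scores. Text and table then agree. If time to first 0 is of interest, derive it from the complete series.

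Treatment and sample size do not change. A pain-free patient answers one more 0-10 question per scheduled day. On Days 1-14 pain medication is recorded anyway, and Days 30, 90 and 180 already have a LANSS contact. Days 60, 120 and 150 are VAS-only, so the added burden is at most three extra contacts per pain-free patient.

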APPENDIX I - Eastern Cooperative Oncology Group (ECOG) Performance Status

GRADE	ECOG PERFORMANCE STATUS
0	Fully active, able to carry on all pre-disease performance without restriction
1	Restricted in physically strenuous activity but ambulatory and able to carry out work of a light or sedentary nature, e.g., light house work, office work
2	Ambulatory and capable of all selfcare but unable to carry out any work activities; up and about more than 50% of waking hours
3	Capable of only limited selfcare; confined to bed or chair more than 50% of waking hours
4	Completely disabled; cannot carry on any selfcare; totally confined to bed or chair
5	Dead

APPENDIX II – Visual Analogue Scale Pain Score

UNIVERSAL PAIN ASSESSMENT TOOL

This pain assessment tool is intended to help patient care providers assess pain according to individual patient needs. Explain and use 0-10 Scale for patient self-assessment. Use the faces or behavioral observations to interpret expressed pain when patient cannot communicate his/her pain intensity.

Appendix III – MD Anderson Symptom Inventory (MDASI) Questionnaire

M. D. Anderson Symptom Inventory (MDASI) Core Items

Part I. How severe are your symptoms?

People with cancer frequently have symptoms that are caused by their disease or by their treatment. We ask you to rate how severe the following symptoms have been *in the last 24 hours*. Please fill in the circle below from 0 (symptom has not been present) to 10 (the symptom was as bad as you can imagine it could be) for each item.

	Not Present										As Bad As You Can Imagine	
	0	1	2	3	4	5	6	7	8	9	10	
1. Your pain at its WORST ?												
2. Your fatigue (tiredness) at its WORST ?												
3. Your nausea at its WORST ?												
4. Your disturbed sleep at its WORST ?												
5. Your feelings of being distressed (upset) at its WORST ?												
6. Your shortness of breath at its WORST ?												
7. Your problem with remembering things at its WORST ?												
8. Your problem with lack of appetite at its WORST ?												
9. Your feeling drowsy (sleepy) at its WORST ?												
10. Your having a dry mouth at its WORST ?												
11. Your feeling sad at its WORST ?												
12. Your vomiting at its WORST ?												
13. Your numbness or tingling at its WORST ?												

Appendix IV – Leeds Assessment of Neuropathic Symptoms and Signs (LANSS) scale

The S-LANSS Pain Score

1. In the area where you have pain, do you also have "pins and needles", tingling or prickling sensations?	
 NO – I don't get these sensations	0
 YES – I get these sensations	5
2. Does the painful area change colour (perhaps look mottled or more red) when the pain is particularly bad?	
 NO – The pain does not affect the colour of my skin	0
 YES – I have noticed that the pain does make my skin look different from normal.	5
3. Does your pain make the affected skin abnormally sensitive to touch? Getting unpleasant sensations or pain when lightly stroking the skin might describe this.	
 NO – The pain does not make my skin abnormally sensitive to touch.	0
 YES – My skin in that area is particularly sensitive to touch.	3
4. Does your pain come on suddenly and in bursts for no apparent reason when you are completely still? Words like "electric shocks", jumping and bursting might describe this.	
 NO – My pain doesn't really feel like this.	0
 YES – I get these sensations often.	2
5. In the area where you have pain, does your skin feel unusually hot like a burning pain?	
 NO – I don't have burning pain	0
 YES – I get burning pain often	1
6. Gently rub the painful area with your index finger and then rub a non-painful area (for example, an area of skin further away or on the opposite side from the painful area). How does this rubbing feel in the painful area?	
 The painful area feels no different from the non-painful area	0
 I feel discomfort, like pins and needles, tingling or burning in the painful area that is different from the non-painful area.	5
7. Gently press on the painful area with your finger tip and then gently press in the same way onto a non-painful area (the same non-painful area that you chose in the last question). How does this feel in the painful area?	
 The painful area does not feel different from the non-painful area.	0
 I feel numbness or tenderness in the painful area that is different from the non-painful area.	3
Total score:	

Scoring a score of 12 or more suggests pain of predominantly neuropathic origin

